6.5.2 Extent of Exposure

Extent of exposure (days) = date of last drug taken – date of first drug taken + 1

If the date of first drug taken is not available, the date when the drug was firstly dispensed will be used for calculation.

If the date of last drug taken is not available, the date will be replaced with that of the last drug return, previous drug taken, or previous drug return in order.

6.5.3 Mean Daily Dose

Descriptive statistics of mean daily dose of the test drug will be presented by center, and treatment.

$$\text{Mean daily dose} = \frac{\text{Number of study medication taken}}{\text{Extent of exposure (section 6.5.2)}}$$

6.6 Analysis of Efficacy

6.6.1 Primary Efficacy Endpoint

An improvement of 40% or greater response rate from baseline in treatment group is considered effective and worth further study. The endpoint will be analyzed by checking if the difference of counts of responder is larger than 0 between PDC-1421 arm and placebo arm. Missing data caused by premature termination will be utilized the last observation carried forward (LOCF).

The response rate in the ADHD-RS-IV total score is defined as the following formula.

$$\text{Response rate} = \frac{\text{score}_{\text{visit}} - \text{score}_{\text{baseline}}}{\text{score}_{\text{baseline}}}$$

and the responder is defined as

$$\text{Responder : response rate} \geq 40\%$$

The descriptive statistics will include the proportion of subjects who achieved at least 40% improvement of the ADHD-RS-IV total score at Visit 6 by treatment group and placebo group. The frequency distribution of pre-treatment and post-treatment will also be tabulate and report in bar graph.

The primary measure of efficacy was the ADHD-RS-IV, consisting of 18 items designed to reflect current symptomatology of ADHD based on DSM-IV-TR criteria. Each item is scored on a 4-point scale ranging from 0 (reflecting no symptoms) to 3 (reflecting sever symptoms) with total scores ranging from 0 to 54, which is calculated by summing up scores of subscales. The 18 items may be grouped into 2 subscales:

- For inattention (IA) subscale raw score: Add the odd-numbered 9 items. Higher score indicate severe inattention symptoms.
- For hyperactivity-impulsivity (HI) subscale raw score: Add the even-numbered 9 items. Higher score indicate severe hyperactivity-impulsivity symptoms.
- To obtain the total raw score: Add the IA and HI subscale raw scores.

Following SAS procedures will be applied for chi-Square test between arms.

```
%macro;  
proc freq data = ____;  
    table response*treatment/chisq;  
    output out = chiqtest chisq;  
run;  
%mend;
```

When there has a missing value issue, the following LOCF SAS procedures will be applied.

```
%macro;  
DTAT locf1;  
    LENGTH dtype $15;  
    RETAIN retain;  
    SET lab;  
    BY usubjid visit;  
  
    IF FIRST . visit ^=0 THEN retain = . ;  
    IF qsstresc NE . THEN retain = qsstresc;  
    IF qsstresc= . THEN DO;  
        qsstresclocf = retain;  
        dtype = 'LOCF';  
    END;  
    ELSE qsstresclocf = qsstresc;  
RUN;  
%mend;
```

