8.1 Sample Size Determination

In part II, this is a small proof-of-concept study to evaluate low-dosed PDC-1421 arm, high-dosed PDC-1421 arm and placebo arm in the treatment of ADHD. A two stage design developed by Jung (2008) with $\alpha=0.15$ and power=80% will be used. We estimated that the PDC-1421 is considered non-effective if the response rate based on ADHD Rating Scale – Investigator Rated (ADHD-RS-IV) is 20 % or lower and is worth further study if the response rate is 40 % or higher. At the first stage, we recruit 23 subjects for each group. If the difference between the numbers of responders for any PDC-1421 arm and control arm is greater or equal to 0, we proceed to the second stage. We will recruit 10 subjects for each group at the second stage. If the difference between the accumulated numbers of responders for any PDC-1421 arm and control arm is less than 4, we reject the drug. The minimum sample size required is to recruit 69 subjects, while the maximum sample size is 99. No multiple comparison will be applied.

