5.3.4 Determination of Sample Size

A two stage design developed by Jung (2008) with significant level $\alpha = 0.15$ and power = 80%.

$$\text{Effect of PDC - 1421 : } \begin{cases} \text{Non-effective , if Response Rate } \leq 20\% \\ \text{Worth further study, if Response Rate } \geq 40\% \end{cases}$$

Stage I	Numbers of responders	Stage II
High-Dose (2 PDC-1421 Capsules) (23 subjects)	$H - P \geq 0$	Add 10 subjects and proceed to stage II
Low-Dose (1 placebo, 1 PDC-1421) (23 subjects)	$L - P \geq 0$	Add 10 subjects and proceed to stage II
Placebo (2 placebo capsules) (23 subjects)		Add 10 subjects and proceed to stage II

If the difference between the accumulated numbers of responders for any PDC-1421 arm and control arm is less than 4, we reject the drug. The minimum sample size required is to recruit 69 subjects, while the maximum sample size is 99.

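### SAP 6.6.1 can be read as setting an uncontrolled 40% pass mark for a dose arm, uses response rate in a second sense, and does not say which responder rule decides

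*SAP*

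**What the plan says.** **Sizing and decision rule.** Protocol 8.1 specifies a two-stage design with alpha 0.15 "and power=80% will be used". The drug is taken as non-effective if the response rate "is 20 % or lower and is worth further study if the response rate is 40 % or higher". These are assumed true shares of responders. The decision itself is a count comparison with placebo. "At the first stage, we recruit 23 subjects for each group", and the trial continues if a PDC-1421 arm has at least as many responders as placebo. Ten more per group are then added. SAP 5.3.4 repeats this and gives the final rule: "If the difference between the accumulated numbers of responders for any PDC-1421 arm and control arm is less than 4, we reject the drug".

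**Endpoint.** Protocol 3.2 and SAP 5.3.2 define the primary endpoint as an ADHD-RS-IV improvement of at least 40% from baseline, which is a threshold for one subject.

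**Primary analysis.** SAP 6.6.1 makes four statements in turn:

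1. "An improvement of 40% or greater response rate from baseline in treatment group is considered effective and worth further study".
2. The endpoint is analysed by checking whether the responder count on PDC-1421 exceeds that on placebo by more than 0.
3. "The response rate in the ADHD-RS-IV total score is defined as the following formula". The formula is a subject's visit score minus baseline score, divided by baseline score.
4. A responder is a subject whose response rate, in that sense, is at least 40%.

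**Later change.** SAP 5.4 says the study was terminated because the interim results did not meet the protocol's requirement, and that the chi-square and Wilcoxon tests between arms will not be done.

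**The concern.** Two different 40% figures meet in the opening sentence of SAP 6.6.1. One is the subject-level responder threshold. The other is the true arm-level rate assumed for sizing. The sentence attaches a verdict of effectiveness to a before-after figure in the treatment group and leaves placebo out. Because response rate is then redefined per subject, the reader cannot tell whether 40% describes a person or an arm.

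An assumed true rate is not a sensible observed threshold. An arm that truly performs at that rate falls below it about half the time through sampling alone. A threshold without a comparator also responds to the general level of response, not to a drug effect.

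The second sentence brings placebo back, but with a third cut-off beside the two in SAP 5.3.4. The section does not say whether the 40% sentence replaces this check, adds to it or merely introduces it. At stake is whether the study report could call a dose effective, or dismiss it, on a rule other than the one the trial was sized for.

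**Working it through.** **Inputs.** From Protocol 8.1 and SAP 5.3.4: 23 per arm at stage 1, 10 more at stage 2 (33 in total); continue if the difference is at least 0; reject if the cumulative difference is below 4; design rates 20% and 40%. Assumption: placebo responds at 20%, since the documents give no separate placebo rate. All figures are per dose.

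**1. Reproduce the design.** Let D1 and D2 be the differences in responders (active minus placebo) in stages 1 and 2, each a difference of two independent binomials. A dose passes with probability

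P(D1 ≥ 0 and D1 + D2 ≥ 4) = Σ over d ≥ 0 of P(D1 = d) × P(D2 ≥ 4 − d).

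- 40% against 20%: 0.801 (stated power 80%).
- 20% against 20%: 0.139 (within the stated alpha of 0.15; a cut-off of 3 would give 0.216).

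The count rule is therefore the rule that carries the stated error rates.

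**2. The opening sentence as a group pass mark.** The smallest count giving at least 40% is:

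- n = 23: 0.4 × 23 = 9.2, so 10. P(X ≥ 10 | 23, 0.40) = 0.444.
- n = 33: 0.4 × 33 = 13.2, so 14. P(X ≥ 14 | 33, 0.40) = 0.453.

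No placebo assumption enters here. Requiring the stage 1 continuation as well (placebo 20%) changes 0.453 only to 0.451.

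**3. How often the two rules disagree (40% against 20%).** The probability of passing the count rule and also reaching 14 of 33 is 0.442. So a dose passes the count rule but misses the bar with probability 0.801 − 0.442 = 0.359. At n = 23, a difference above 0 has probability 0.912, and that together with at least 10 responders has 0.442. The gap is 0.470.

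**4. A dose no better than placebo.**

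| True rate in both arms | 40% bar, n = 33 | Count rule |
|---|---|---|
| 20% | 0.003 | 0.139 |
| 30% | 0.088 | 0.171 |
| 40% | 0.453 | 0.187 |

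The bar is stricter than the planned rule at 20% and 30%, and much looser at 40%.

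**5. The above-0 check against the planned cut-offs.**

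| Check | 40% against 20% | 20% against 20% |
|---|---|---|
| Difference at least 0, n = 23 | 0.953 | 0.574 |
| Difference above 0, n = 23 | 0.912 | 0.426 |
| Difference above 0, n = 33 | 0.953 | 0.439 |
| Planned two-stage rule | 0.801 | 0.139 |

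At stage 1, at least 0 and above 0 differ only on a tie, which has probability 0.953 − 0.912 = 0.041 or 0.574 − 0.426 = 0.148. At the end the gap is large: an above-0 check at n = 33 would pass a dose with no effect 0.439 of the time, against 0.139.

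**The case against.** The strongest reply is that the opening sentence is not a decision rule. It echoes the design hypothesis of Protocol 8.1 and the subject-level endpoint wording, and may simply be a garbled merger of the two. No passage says that an arm passes if its observed share reaches 40%. The next sentence, the only one in SAP 6.6.1 that says how the endpoint is analysed, is placebo-controlled, and SAP 5.3.4 keeps the cut-off of 4. Most of this stands: the intent cannot be settled from the text, and the 0.444 and 0.453 apply only if the sentence is used as a group pass mark. It does not clear the section, however. The sentence delivers a verdict on a group, the responder definition is given separately, and the controlled check that follows does not match SAP 5.3.4.

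Three stronger readings are tempting but not supported:

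- A reader might infer that the SAP has replaced the controlled rule with an uncontrolled one. The second sentence of SAP 6.6.1 and the whole of SAP 5.3.4 contradict that.
- A reader might infer that SAP 5.4 leaves the 40% bar as the only criterion. It drops the chi-square and Wilcoxon tests, not the responder-count comparison. The stated reason for stopping points to the count rule, which is the only interim requirement that Protocol 8.1 sets.
- A reader might combine the sentence with the per-subject formula and infer a required mean improvement of 40% in the arm. Nothing in SAP 6.6.1 tests an arm mean.

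**Conclusion.** The concern holds as an ambiguity and an inconsistency that should be corrected. SAP 6.6.1 uses response rate in a different sense from SAP 5.3.4 and Protocol 8.1, opens with a sentence that can be taken as an uncontrolled pass mark, and adds a third between-arm cut-off without saying which one decides.

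Conditional on the pass-mark reading, a dose at the design alternative would succeed with probability 0.444 (n = 23) or 0.453 (n = 33), not 0.801. The 0.801 assumes 20% on placebo; the other two figures do not. Because the trial stopped after the interim, the n = 23 figure is the one closest to the data, though the number actually analysed may differ from 23 per arm.

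It would be too strong to say that the bar generally favours an ineffective dose. It does so if both arms respond at about 40% (0.45 against 0.19), which is twice the assumed placebo rate, and the reverse holds at 30% (0.09 against 0.17). The documents do not show that the 40% sentence was ever used to make a decision.

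**What to change.** In SAP 6.6.1:

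1. Delete the opening sentence.
2. Define a responder as a subject whose ADHD-RS-IV total has improved, that is fallen, by at least 40% from baseline at Visit 6. The direction needs stating because the printed formula gives a negative value when the score falls.
3. Call the per-subject quantity *percent improvement*, calculated as (baseline − visit) / baseline, and keep *response rate* for an arm's share of responders.
4. Replace the above-0 check with the rules of SAP 5.3.4 and Protocol 8.1: difference of at least 0 at stage 1, and reject if the cumulative difference is below 4.
5. State that only this comparison with placebo decides whether a dose merits further study.

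Deleting the first sentence alone would leave the conflict over the cut-off in place. The cost is an SAP wording change, with no new data and no further patients. As the SAP is already final, it can be made as a short amendment, with the same definitions carried into the study report.

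### SAP 6.6.1 judges the primary endpoint by a responder-count lead above 0 with no stage named, contradicting the staged cut-offs (0, then 4) of Protocol 8.1 and SAP 5.3.4

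*SAP*

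**What the plan says.** Protocol 8.1 sets a two-stage rule on the difference in number of responders between a PDC-1421 arm and placebo.

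- **Stage I, 23 per arm:** if the difference for any PDC-1421 arm "is greater or equal to 0, we proceed to the second stage".
- **End, 33 per arm:** SAP 5.3.4 repeats the protocol's final cut-off: "If the difference between the accumulated numbers of responders for any PDC-1421 arm and control arm is less than 4, we reject the drug". It also tabulates the stage I condition for each dose, as a high-dose or low-dose minus placebo difference of at least 0.

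SAP 6.6.1 then describes the primary analysis: "The endpoint will be analyzed by checking if the difference of counts of responder is larger than 0 between PDC-1421 arm and placebo arm". It does not say whether this applies at the interim or at the end, and it does not mention 4.

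SAP 5.4 states that the analysis follows the protocol, that the interim results did not meet the protocol's requirement, that the study was terminated, and that the between-arm tests will not be run. The only SAP version listed in 8.2 is dated April 25, 2024.

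**The concern.** A strictly positive difference is neither of the two stated cut-offs. At the interim it is stricter than the protocol: a tied dose continues under Protocol 8.1 and fails under SAP 6.6.1. At the end it is looser: a lead of 1, 2 or 3 responders satisfies 6.6.1 and is a rejection under 5.3.4.

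SAP 5.4 drops the chi-square test, so the count comparison is the only between-arm criterion left for the primary endpoint, and the SAP states it in two incompatible ways. The stated reason for termination is that the interim missed the protocol's requirement. A reader cannot confirm this without knowing the counts and the cut-off used.

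**Working it through.** **Inputs.** All are from Protocol 8.1, repeated in SAP 5.3.4.
- Design targets: "A two stage design developed by Jung (2008) with $\alpha=0.15$ and power=80% will be used".
- Response rates: the drug is non-effective if its rate "is 20 % or lower and is worth further study if the response rate is 40 % or higher". I take 20% as the common null rate and as the placebo rate under the alternative.
- Sizes: "At the first stage, we recruit 23 subjects for each group"; "We will recruit 10 subjects for each group at the second stage".

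**Step 1. Reproduce the stated design.** Let D1 be the responder difference (dose minus placebo) after stage I, and D2 the difference among stage II subjects. Each is a difference of two independent binomials, with n = 23 and n = 10 per arm. For final cut-off c,

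P(success) = Σ P(D1 = i) · P(D2 = j), summed over i ≥ 0 and i + j ≥ c.

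| Final cut-off c (stage I gate ≥ 0) | Type I error, 20% vs 20% | Power, 40% vs 20% |
|---|---|---|
| 1 (i.e. > 0) | 0.4005 | 0.932 |
| 3 | 0.216 | 0.864 |
| **4** | **0.139** | **0.801** |
| 5 | 0.082 | 0.719 |

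Only c = 4 keeps type I error at or below 0.15 with power of at least 80%. Raising the gate to > 0 while keeping c = 4 gives 0.135 and 0.792, just under the stated power. The stated operating characteristics therefore belong to the 0-then-4 rule.

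**Step 2. The interim.** Let b be the binomial probability and F the binomial cumulative distribution, both with n = 23. With placebo at 20%, the chance that at least one dose reaches cut-off c is

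1 − Σₓ b(x; 0.20) · F(x + c − 1; p_low) · F(x + c − 1; p_high),

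where c = 0 is the protocol rule and c = 1 is the 6.6.1 rule.

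| True rates | ≥ 0 (Protocol 8.1) | > 0 (SAP 6.6.1) | Rules disagree |
|---|---|---|---|
| Both doses 20% | 0.7335 | 0.5915 | 0.142 |
| One dose 40%, other 20% | 0.9611 | 0.9224 | 0.039 |
| Both doses 40% | 0.9895 | 0.9747 | 0.015 |

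The last column is the subtraction of the two before it. It equals the probability that the better dose ties exactly with placebo, which is the only case in which the two wordings give different decisions for the trial.

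**Step 3. The end of stage II (hypothetical).** All arms are at 20%, with a shared placebo arm. The result depends slightly on whether each dose must pass its own stage I gate or one passing dose carries both forward.

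| Final cut-off | Gate | False go, per dose | False go, at least one dose |
|---|---|---|---|
| > 0 | each dose separately | 0.400 | 0.563 |
| > 0 | one passing dose carries both | 0.419 | 0.568 |
| ≥ 4 | each dose separately | 0.139 | 0.231 |
| ≥ 4 | one passing dose carries both | 0.139 | 0.232 |

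With separate gates, the per-dose 0.400 changes little with the common response rate: 0.392 at 10% and 0.404 at 50%.

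**The case against.** The strongest reply is that the SAP already points to the right rule. Section 5.3.4 gives both cut-offs and the action attached to each. Section 5.4 says the analysis follows the protocol and describes the termination as a failure to meet the protocol's requirement, which at stage I means at least 0. The sentence in 6.6.1 attaches no continue or reject action, and nothing shows that it was used at the interim. This stands. The defect is an internal contradiction in the SAP, and the protocol rule has not been replaced.

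The second reply is that the false-go figure of about 40% cannot arise here. It needs a decision at 33 per arm, and the only listed SAP version already records termination at the interim. This also stands, so Step 3 is counterfactual and only shows how far the wording departs from the design.

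A reader might go further and infer that the trial was stopped wrongly. The documents do not support that. They give no interim counts, no tie is shown, and 5.4 names the protocol as the standard applied.

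The replies do not remove the conflict. Section 6.6.1 is the operative section for the primary endpoint, and a reader who finds two cut-offs there and in 5.3.4 cannot tell from the text alone which one produced the reported decision.

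**Conclusion.** The conflict is real and should be corrected, but its practical reach is confined to the interim decision. It matters only if the better dose tied with placebo. At the design rates, the chance of that is 14% when both doses are inactive, 3.9% when one dose truly has 40%, and 1.5% when both do. Had stage II run and 6.6.1 governed, an inactive dose would have passed with probability 0.400 (0.419 if one passing dose carries both), against 0.139 under the planned rule. That figure describes the wording and is not an error the trial incurred.

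These results assume exact binomial counts, a 20% placebo rate and equal arms of 23 and then 10. The 0.139 depends on the 20% rate: it is 0.073 at a common rate of 10% and 0.171 at 30%. The count cut-offs also presume equal arms. The ITT definition in SAP 5.3.1 can remove randomised subjects, so analysed arm sizes may differ. This applies equally to the protocol's own rule.

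**What to change.** 1. Replace the sentence in SAP 6.6.1 with the staged cut-offs already in Protocol 8.1 and SAP 5.3.4: at stage I, proceed if the responder difference from placebo is at least 0 for any PDC-1421 arm; at the end, reject the drug if the cumulative difference is below 4.
2. In the study report, give the interim responder count and denominator for each arm and state which cut-off was applied.
3. If the better dose tied with placebo, correct the stated reason for termination, because a tie meets the protocol's stage I requirement.
4. If ITT arm sizes differ, also show the difference in proportions as a descriptive check. It should not become a new decision rule, since no operating characteristics have been worked out for it.

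The cost is one sentence of SAP text, one check of the interim table and a short statement in the report. No new data are needed.

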3.2 Primary Endpoint

Improvement of 40% or greater in ADHD Rating Scale-Investigator Rated (ADHD-RS-IV) from baseline up to 8 weeks treatment.

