6.2 Methods and Timing for Assessing, Recording, and

Analyzing of Efficacy Parameters.

The data obtained from eligible subjects before study drug administration in Visit 2 or Visit 1 (if no data at Visit 2) are set as baseline. After the beginning of treatment, the collection of data of efficacy parameters are performed at planned treatment schedule as [section 5.2](#). CRC shall record these data in CRF in detail after each visit during the treatment period. In part II, data comparison between group of 1 capsule TID, 2 capsules TID of PDC-1421 Capsule and 2 capsules TID of placebo will be conducted in final report of this study to evaluate which group(s) of PDC-1421 Capsule are efficient. The rating scales are as follows:

- **ADHD-RS-IV**

The ADHD-RS-IV with Adult Prompts is an 18-item scale base on the DSM-IV-TR' criteria for ADHD that provides a rating of the severity of symptoms¹⁵. The adult prompts serve a guide to explore more fully the extent and severity of ADHD symptoms and create a framework to ascertain impairment. The odd-numbered 9 items assess inattentive symptoms and the even-numbered 9 items assess hyperactive-impulsive symptoms. Scoring is based on a 4-point, yielding a possible total score of 0 – 54. Likert-type severity scale: 0 = Never or Rarely, 1 = Sometimes, 2 = Often, 3 = Very Often. Clinicians should score the highest score that is generated for the

prompts for each item.

For inattention (IA) subscale raw score: Add the odd-numbered 9 items

For hyperactivity-impulsivity (HI) subscale raw score: Add the even-numbered 9 items

To obtain the total raw score: Add the IA and HI subscale raw scores.

- **Clinical Global Impression¹⁶**

At the baseline visit, clinicians completed the CGI-S and were asked to evaluate the severity of subjects' illness with respect to ADHD symptoms based on the clinician's experience with this particular population. Possible scores ranged from 1 (normal, not at all ill) to 7 (among the most extremely ill). At all subsequent study visits, clinicians used the CGI-I to rate the subjects' total improvement based on comparison with their baseline assessment from 1 (very much improved) to 7 (very much worse).

- **CAARS-S:S**

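### Read literally, the SAP's responder formula counts ADHD-RS-IV worsening, not improvement; the Visit 6 responder table and the interim counts need a documented sign check

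*SAP*

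**What the plan says.** Protocol 3.2 gives the primary endpoint as "Improvement of 40% or greater in ADHD Rating Scale-Investigator Rated (ADHD-RS-IV) from baseline up to 8 weeks treatment". The protocol offers no formula for it, and SAP 5.3.2 restates it in words only.

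SAP 6.6.1 holds the only operational definition. It announces that "The response rate in the ADHD-RS-IV total score is defined as the following formula" and displays visit score minus baseline score, divided by baseline score. A responder is a subject for whom this is at least 40%. No absolute value or sign convention is given.

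The same section fixes the direction of the scale: "Each item is scored on a 4-point scale ranging from 0 (reflecting no symptoms) to 3 (reflecting sever symptoms". For the inattention subscale it adds "Higher score indicate severe inattention symptoms", and it says the same of the hyperactivity-impulsivity subscale. The total is the sum of the two, with protocol 6.2 "yielding a possible total score of 0 – 54". Remission is a total of 18 or less (protocol 3.3, SAP 5.3.2), so lower is better. The planned summary in SAP 6.6.1 is the "proportion of subjects who achieved at least 40% improvement of the ADHD-RS-IV total score at Visit 6".

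Responder counts feed the two-stage rule in protocol 8.1 and SAP 5.3.4. After 23 subjects per arm the trial continues if either active arm has at least as many responders as placebo. After 33 per arm the drug is rejected if the accumulated difference is below 4. SAP 5.4 reports that the interim did not meet the protocol's requirement, that the study was terminated, and that the between-arm tests will not be run. SAP 8.2 lists a single version, approved 25 April 2024.

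**The concern.** The formula and the words around it point in opposite directions. On a scale where more is worse, a subject who improves has a visit score below baseline, so the displayed quantity is negative and cannot reach +40%. Only a subject who deteriorates can reach it.

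This is the variable behind the primary endpoint. A programmer who implements it literally, or a validator who checks output against the SAP, would tabulate deterioration under the label of response. Between arms, the group with more worsening would look better. Any decision based on such counts would carry the opposite meaning from the one intended.

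**Working it through.** **The plan's own design figures.** Protocol 8.1 gives alpha 0.15, power 80%, response rates of 20% and 40%, 23 + 10 subjects per arm, continuation if the stage I difference D1 ≥ 0, and rejection of the drug if D1 + D2 < 4. For one active arm against placebo, the probability of not rejecting the drug is the sum of P(D1)·P(D2) over D1 ≥ 0 and D1 + D2 ≥ 4, where each D is a difference of two independent binomials.

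- 40% against 20%: 0.801, which reproduces the stated 80%.
- 20% against 20%: 0.139, within the stated 0.15.

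The planning rates refer to improvement, so correcting the sign changes neither figure.

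**The formula.** Let B be the baseline total and V the visit total.

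- As written: r = (V - B)/B, responder if r ≥ 0.40, which means V ≥ 1.4B.
- As the endpoint is worded: p = (B - V)/B, responder if p ≥ 0.40, which means V ≤ 0.6B.

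Since p = -r, no subject with B > 0 can satisfy both.

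| Baseline → visit | r as written | Responder as written | p | Responder by the protocol's wording |
|---|---|---|---|---|
| 35 → 21 | (21 - 35)/35 = -0.40 | no | +0.40 | yes |
| 30 → 18 (also in remission) | (18 - 30)/30 = -0.40 | no | +0.40 | yes |
| any → 0 | -1.00 | no | +1.00 | yes |
| 35 → 49 | (49 - 35)/35 = +0.40 | yes | -0.40 | no |

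**The ceiling.** The scale stops at 54, and 54/1.4 = 38.57. From baseline 38 a 40% worsening still fits (38 × 1.4 = 53.2). From 39 it does not (39 × 1.4 = 54.6). A subject with a baseline of 39 or more could never be a responder as written.

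**All possible score pairs.** Take whole-number baselines 28 to 54 and visit scores 0 to 54, which gives 27 × 55 = 1,485 pairs. The lower limit is the screening minimum in inclusion criterion 6. The worded definition is met by 680 pairs, the written one by 92, and both by 0. These are counts of pairs, not expected numbers of subjects. The zero overlap does not depend on the lower limit of 28.

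**Part I as an illustration.** Protocol 1.3.2 reports that 5 of 6 subjects improved by at least 40%. The written formula would count none of those five.

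**What the formula can reach.** The SAS code in SAP 6.6.1 tabulates a variable named response and does not derive it, so the documents do not show which sign was programmed. Stage II did not take place, so the final rule is no longer applied, and SAP 5.4 drops the between-arm tests. Two outputs remain: the Visit 6 responder table and the interim responder counts already acted on.

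**The case against.** The strongest reply is that nobody would be misled. SAP 6.6.1 speaks of improvement on both sides of the formula, protocol 3.2 and SAP 5.3.2 do the same, and remission at 18 or less confirms the direction. A competent programmer would take the fall in score and never notice the slip. That stands as far as it goes: the intent is not in doubt, and nothing in the documents shows that any subject was misclassified. It does not make the formula right, because the formula is the only operational definition of the primary endpoint and nothing else in either document overrides it.

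The second reply concerns timing. The one listed SAP version already reports the interim result and the termination. The rule then in force, protocol 8.1, contains no formula. This also stands. A reader might infer that the trial was stopped because worsening was counted as response. The documents do not support that: they do not say how responders were derived at the interim, and they give no interim counts. They do not exclude it either, which is why a check is worth asking for.

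A reader might also infer that a stage II decision still depends on this formula. It does not, because the study ended before stage II.

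A minus sign or absolute-value bar could have been lost in reproducing the formula. Nothing in the text suggests it, but a look at the approved SAP page would settle it.

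**Conclusion.** The formula in SAP 6.6.1 is wrong as written and should be corrected. Taken literally it reverses the primary endpoint completely: no possible score pair is a responder under both definitions, and response is impossible from baseline 39 up. This rests only on the scale direction and range that the documents state.

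The practical harm is conditional on the formula having been programmed literally. If it was, the Visit 6 responder table is reversed in meaning, and so are the interim counts if they used the same derivation. If the programs took baseline minus visit, the error is confined to the SAP text. The documents cannot separate these cases. The protocol's worded endpoint and the design figures are unaffected.

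A lesser point concerns terms. SAP 6.6.1 uses 'response rate' for a subject's percent change, while protocol 8.1 and SAP 5.3.4 use it for the share of responders in an arm. Both carry a 40% threshold, so the two are easily confused.

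**What to change.** In SAP 6.6.1, replace the formula and the cut-off with:

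- Percent improvement = (baseline score - Visit 6 score) / baseline score × 100, using the LOCF value under the plan's existing rule where Visit 6 is missing.
- Responder = percent improvement of at least 40%.

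Keep 'response rate' for the proportion of responders in an arm.

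Then document a check that the interim responder count and the final responder table were both derived with this sign. If either was not, correct it and report the corrected counts.

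The cost is one formula, recorded as a correction to a finalised SAP, and a review of two derivations. No new data are needed. Rerunning output is necessary only if the check fails.
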